6.1.5 Compliance

The IMP will be administered periodically in the study by the investigator, thus, monitoring of subject compliance with IMP administration is not applicable.

Drug accountability records, documenting that the subject received allocated IMP administration, will be maintained by the investigator.

6.2 Procedures Associated with Investigational Medicinal Product Administration

6.2.1 Antibiotic Prophylaxis

All subjects must receive appropriate prophylactic antibiotics CCI

- Treatment 1:
 - antibiotics must be adapted based on screening culture and sensitivity.
- Retreatments:
 - antibiotics may be empiric or adapted.

See [Section 6.4.1.2](#) for full details on antibiotic prophylaxis within the study.

The choice of antibiotic, dose, and start and stop dates must be recorded in the eCRF.

6.2.2 Anticoagulant/Antiplatelet Usage

Medications with anticoagulant effects must be stopped at least 3 days prior to IMP administration and only restarted on the day following IMP administration. They may be stopped for a longer period if deemed necessary in the opinion of the investigator. These medications include but are not limited to:

- Warfarin and other coumadin derivatives
- Acetylsalicylic acid (including low-dose aspirin)
- Clopidogrel/ticlopidine.

If medically indicated, low molecular weight heparins are permitted with the last dose of administration 24 hours prior to IMP administration and may be restarted on the day following IMP administration.

6.2.3 Anaesthesia

Local or general anaesthesia may be used if required. The choice of anaesthesia for the treatment procedure should be determined by the investigator and/or anaesthetist (anaesthesiologist) to ensure appropriate safety and comfort for the subject (taking into account factors such as risk of autonomic dysreflexia, spasticity and tolerance to cystoscopic

procedures). It is acceptable to perform the procedure with no anaesthesia if medically appropriate.

The following anaesthetic options (either alone or in combination) are permitted:

- (a) Local anaesthesia to the urethra:
 - e.g. intra-urethral lidocaine gel (or similar local anaesthetic gel), to facilitate comfortable cystoscope insertion.
- (b) Local anaesthesia to the bladder wall via instillation:
 - e.g. 1 2% lidocaine solution (or similar local anaesthetic solution), to reduce sensation of the intradetrusor injections
 - instilled immediately prior to the procedure and must remain in the bladder for approximately 30 minutes to ensure sufficient anaesthesia
 - prior to commencing the intradetrusor injections the local anaesthetic solution must be drained, then the bladder must be instilled (rinsed) with saline and drained again.
- (c) Sedation:
 - oral, inhalational, or intravenous sedative(s)
 - used per local site practice and if medically required.
- (d) General anaesthesia:
 - light and short duration general anaesthesia
 - used per local site practice and if medically required
 - must be administered by an appropriately qualified anaesthetist (anaesthesiologist)
 - neuromuscular blocking agents are however prohibited.

Details of anaesthetic(s) used must be recorded in the eCRF.

6.2.4 Safety Monitoring During Treatment Administration

Appropriate resuscitation equipment and trained personnel must be available at the site to treat any life-threatening emergencies (e.g. anaphylaxis, autonomic dysreflexia or cardiorespiratory arrest) during the IMP administration and during the immediate post-treatment observation period.

All subjects must be monitored throughout the procedure if sedatives or general anaesthesia are being used, per local site practice.

In addition, subjects with SCI with a vertebral lesion above T6 are at a greater risk of developing autonomic dysreflexia during invasive procedures [19]. Therefore, these subjects must:

- Have their blood pressure (BP) and heart rate (HR) continually monitored throughout the treatment administration procedure. There is no need to record BP or HR monitoring data, other than abnormalities that are clinically significant in the investigator's opinion; which should be reported as AEs.

If there are any symptoms or signs of autonomic dysreflexia developing, then:

- Immediate treatment for the autonomic dysreflexia should be instituted per local site practice and appropriate guidelines
- The treatment procedure should be immediately stopped until the autonomic dysreflexia has resolved. The treatment procedure should only be recommenced if deemed clinically safe

- 7) CCI [REDACTED]
[REDACTED]
[REDACTED]
- [REDACTED]
- [REDACTED]
- [REDACTED]
[REDACTED]
[REDACTED]
- [REDACTED]
[REDACTED]
 - | [REDACTED]
 - | [REDACTED]
 - | [REDACTED]
 - | [REDACTED]
 - | [REDACTED]
 - | [REDACTED]
 - | [REDACTED]
 - | [REDACTED]
 - | [REDACTED]
- [REDACTED]
- [REDACTED]
- [REDACTED]
[REDACTED]

CCI

CCI

CCI

6.3.3 Post-treatment Observation

Vital signs should be recorded approximately 30 minutes following the procedure.

If sedation or general anaesthesia was used then post-treatment observation must also be performed according to local site practice (e.g. monitoring of BP and HR until recovered).

For any AEs that occur on the day of treatment/retreatment it should be clearly documented if the AE occurred before or after the treatment procedure.

All subjects must be observed for a minimum of 30 minutes following the IMP administration. Subjects should only leave the clinic when it is safe and appropriate, according to the investigator's judgement and local site practice.

Subjects should be instructed to contact the site if there are any AEs post-treatment.

6.4 Concomitant Medications and Therapies

The following should be recorded in the eCRF:

- Any prior or concomitant NDO therapy or medication given to a subject before Screening or during the study
- Any prior or concomitant non-NDO therapy or medication given to a subject in the 30 days before Screening or during the study.

6.4.1 Permissible Medications and Therapies

The following concomitant medications are permitted but they must be monitored closely and the dose and dose regimen should preferably remain constant throughout the study:

- Oral medication for NDO (e.g. anticholinergics and beta-3 agonists):
 - must be stable for 4 weeks prior to Screening (inclusion criterion #6)
 - must remain stable for at least 12 weeks following the first IMP administration (inclusion criterion #7)
 - preferably should remain stable throughout the study
 - subjects should be counselled to only change these medications following discussion with the investigator. Change in usage will not be considered as a protocol deviation if it occurs after 12 weeks following the first IMP administration.
- Medications/therapies required for other conditions (including for SCI and MS), as long as the treatment has no known interaction with the IMP is not listed in the prohibited medications (Section 6.4.2), or is not expected to have any significant lower urinary tract effects according to clinical judgement of the investigator, that may confound the study results.

6.4.1.1 Clean Intermittent Catheterisation

All subjects in this study have significant bladder dysfunction and voiding difficulty, requiring routine CIC usage to adequately and regularly drain urine from the bladder.

At Screening, subjects must be routinely performing CIC to manage their bladder function, and ensure regular and adequate bladder emptying. CCI [REDACTED]

[REDACTED]

[REDACTED]

[REDACTED]

[REDACTED]

[REDACTED]

The CIC regimen should be maintained throughout the study; CCI [REDACTED]

[REDACTED]

[REDACTED]

[REDACTED]

[REDACTED]

[REDACTED]

[REDACTED]

6.4.1.2 *Antibiotic Prophylaxis*

Antibiotic prophylaxis is required in the study to cover:

(a) All urodynamic procedures:

- CCI [REDACTED]

(b) All IMP cystoscopic treatment administration procedures:

- CCI [REDACTED]

The minimum duration of the antibiotics can be lengthened per clinical judgment of the investigator.

Antibiotics may be:

- Adapted:
 - based on a recent urine culture and sensitivity test from the subject to determine the most appropriate antibiotic.
- Empiric:
 - based on the best judgement of the investigator, using knowledge of the likely bacteria, the individual subject and local antibiotic resistance and sensitivity patterns.
 - the investigator should ensure that there is no potential risk of colonisation with resistant bacteria to the chosen antibiotic (e.g. multiple recent courses of the same class of antibiotic).

Permitted Antibiotics

All oral antibiotics (except aminoglycoside antibiotics) available locally for the treatment of UTIs may be used at the discretion of the investigator.

The investigator must ensure that the subject has no known history of contraindications (e.g. allergy) to any antibiotics that are dispensed during the study.

Appropriate Usage of Prophylactic Antibiotics

CCI [REDACTED]

[REDACTED]

[REDACTED]

Antibiotic Prophylaxis During Screening

CCI [REDACTED]
[REDACTED]
[REDACTED]
[REDACTED]

Antibiotic Prophylaxis During Follow-up

CCI [REDACTED] [REDACTED] [REDACTED] [REDACTED] [REDACTED] [REDACTED] [REDACTED] [REDACTED] [REDACTED] [REDACTED]
[REDACTED]
[REDACTED]
[REDACTED]
[REDACTED]

[REDACTED]
[REDACTED]

CCI

CCI [REDACTED]

[REDACTED]

CCI

6.4.1.3 *Antibiotics for Symptomatic UTI*

Subjects with NDO may demonstrate atypical symptoms for UTI. If there is any suspicion of a UTI then the subject should be immediately commenced on appropriate antibiotics:

- CCI [REDACTED]
[REDACTED]
 - | [REDACTED]
[REDACTED]
[REDACTED]
 - | [REDACTED]
[REDACTED]
- | [REDACTED]
 - | [REDACTED]
[REDACTED]
[REDACTED]
 - | [REDACTED]
[REDACTED]

[REDACTED]
[REDACTED]
[REDACTED]
[REDACTED]

6.4.1.4 *Definition of Urinary Tract Infection*

- CCI [REDACTED]
 - | [REDACTED] [REDACTED]
 - | [REDACTED]
 - | [REDACTED]
 - | [REDACTED]
 - | [REDACTED]
 - | [REDACTED]
- [REDACTED]
[REDACTED]
[REDACTED]
[REDACTED]

6.4.2 *Prohibited Medications/Therapies*

Prohibited throughout the study:

- Treatment at any anatomical location with any BTX (with the exception of IMP treatments and retreatments as part of this study)
- Medications that affect neuromuscular transmission, such as curare-like depolarising agents, lincosamides, polymyxins, anticholinesterases and aminoglycoside antibiotics (exclusion criterion #20).

Prohibited in the 9 months prior to Screening:

- BTX for any urological condition, e.g. detrusor or urethral sphincter treatments (exclusion criterion #11).

Prohibited in the 6 months prior to Screening and throughout the study:

- Capsaicin or resiniferatoxin (exclusion criterion #14).

Prohibited in the 3 months prior to Screening and throughout the study:

- BTX for any non-urological condition (exclusion criterion #12)
- Bladder installation with any pharmacologic agent (exclusion criterion #13).

Prohibited in the 4 weeks prior to Screening and throughout the study:

- Indwelling bladder catheter (exclusion criterion #10)
- Any neuromodulation/electrostimulation usage for urinary symptoms/incontinence (exclusion criterion #15)
- **CCI** [REDACTED]
- Any new investigational drug or device (exclusion criterion #27).

6.4.2.1 Concomitant treatment for Neurogenic Detrusor Overactivity

These data are to be collected at Screening and at other timepoints. In particular, the following should be collected:

- Daily CIC frequency (at Screening, and if there is a clinically significant change in frequency postbaseline)
- Current anticholinergic or beta-3 agonist usage (at Screening, and if there is a change in medication/frequency/dosage postbaseline).

7 ASSESSMENT OF EFFICACY

For the timing of assessments in this study, refer to the schedules in [Table 4](#), [Table 5](#), and [Table 19](#).

7.1 Primary Efficacy Endpoint and Evaluations

See [Section 3.2.1](#).

7.2 Secondary Efficacy Endpoints and Evaluations

See [Section 3.2.2](#) and [Table 19](#).

Table 19 Efficacy Endpoints During Initial Treatment and Retreatment

Measure	Planned timepoints (dependent on timing of retreatments)	Variable	Endpoint
Weekly number of urinary incontinence episodes on 7-day bladder diary	Study Baseline (Screening) or treatment cycle baseline Week 2 Week 6 Week 12 Every 12 weeks thereafter until retreatment EOS Visit.	Weekly number of urinary incontinence episodes	
 • Mean change from study baseline to each subsequent timepoint within the treatment cycle in weekly number of urinary incontinence episodes • Proportion of subjects with no episodes of urinary incontinence (i.e. continence is achieved) at each timepoint • Proportion of subjects with a urinary incontinence response at several levels (i.e. $\geq 30\%$ improvement, $\geq 50\%$ improvement, $\geq 75\%$ improvement etc.) at each timepoint
Total daily urinary frequency (CIC and spontaneous voiding) on 7-day bladder diary	Study Baseline (Screening) or treatment cycle baseline Week 2 Week 6 Week 12 Every 12 weeks thereafter until retreatment EOS Visit	Total daily urinary frequency	Mean change from study baseline to each subsequent timepoint within the treatment cycle in total daily urinary frequency
Daily spontaneous voiding frequency on 7-day bladder diary	Study Baseline (Screening) or treatment cycle baseline Week 2 Week 6 Week 12 Every 12 weeks thereafter until retreatment EOS Visit.	Daily spontaneous voiding frequency	Mean change from study baseline to each subsequent timepoint within the treatment cycle in daily spontaneous voiding frequency

Measure	Planned timepoints (dependent on timing of retreatments)	Variable	Endpoint
Daily CIC frequency on 7-day bladder diary	Study Baseline (Screening) or treatment cycle baseline Week 2 Week 6 Week 12 Every 12 weeks thereafter until retreatment EOS Visit.	Daily CIC frequency	Mean change from study baseline to each subsequent timepoint within the treatment cycle in daily CIC frequency
Total 24-hour voided volume on 1 day of 7-day bladder diary (CIC and spontaneous voiding)	Study Baseline (Screening) or treatment cycle baseline Week 2 Week 6 Week 12 Every 12 weeks thereafter until retreatment EOS Visit.	Total 24-hour voided volume	Mean change from study baseline to each subsequent timepoint within the treatment cycle in total 24-hour voided volume
24-hour voided volume on 1 day of 7-day bladder diary (spontaneous voiding only)	Study Baseline (Screening) or treatment cycle baseline Week 2 Week 6 Week 12 Every 12 weeks thereafter until retreatment EOS Visit.	24-hour voided volume (spontaneous voiding only)	Mean change from study baseline to each subsequent timepoint within the treatment cycle in 24- hour voided volume (spontaneous voiding only)
24-hour voided volume on 1 day of 7-day bladder diary (CIC only)	Study Baseline (Screening) or treatment cycle baseline Week 2 Week 6 Week 12 Every 12 weeks thereafter until retreatment EOS Visit.	24-hour voided volume (CIC only)	Mean change from study baseline to each subsequent timepoint within the treatment cycle in 24- hour voided volume (CIC only)

Measure	Planned timepoints (dependent on timing of retreatments)	Variable	Endpoint
Total volume per void (spontaneous and CIC) on 1 day of 7-day bladder diary	Study Baseline (Screening) or treatment cycle baseline Week 2 Week 6 Week 12 Every 12 weeks thereafter until retreatment EOS Visit.	Total volume per void	Mean change from study baseline to each subsequent timepoint within the treatment cycle in total volume per void
Volume per void (spontaneous voiding only) on 1 day of 7-day bladder diary	Study Baseline (Screening) or treatment cycle baseline Week 2 Week 6 Week 12 Every 12 weeks thereafter until retreatment EOS Visit.	Volume per void (spontaneous voiding only)	Mean change from study baseline to each subsequent timepoint within the treatment cycle in volume per void (spontaneous voiding only)
Volume per void (CIC only) on 1 day of 7-day bladder diary	Study Baseline (Screening) or treatment cycle baseline Week 2 Week 6 Week 12 Every 12 weeks thereafter until retreatment EOS Visit.	Volume per void (CIC only)	Mean change from study baseline to each subsequent timepoint within the treatment cycle in volume per void (CIC only)
MCC measured by urodynamic filling cystometry	Study Baseline (Screening), Week 6	MCC	Mean change from study Baseline to Week 6 in MCC
MDP during storage measured by urodynamic filling cystometry	Study Baseline (Screening), Week 6	MDP	Mean change from study Baseline to Week 6 in MDP
Vol@1 st IDC measured by urodynamic filling cystometry	Study Baseline (Screening), Week 6	Vol@1 st IDC	Mean change from study Baseline to Week 6 in Vol@1 st IDC
PdetMax@1 st IDC measured by urodynamic filling cystometry	Study Baseline (Screening), Week 6	PdetMax@1 st IDC	Mean change from study Baseline to Week 6 in PdetMax@1 st IDC
Presence of IDCs measured by urodynamic filling cystometry	Study Baseline (Screening), Week 6	Presence of IDCs	Proportion of subjects with no IDCs on urodynamic assessment (i.e. urodynamic cure is achieved)

Measure	Planned timepoints (dependent on timing of retreatments)	Variable	Endpoint
EFP measured by urodynamic filling cystometry	Study Baseline (Screening), Week 6	EFP	Mean change from study Baseline to Week 6 in EFP
DC measured by urodynamic filling cystometry	Study Baseline (Screening), Week 6	DC	Mean change from study Baseline to Week 6 in DC
Treatment response according to I-QoL total and domain summary score	Study Baseline (Treatment Visit) or baseline Week 6 Week 12 EOS Visit.	I-QoL total and domain summary score	Mean change from study baseline to each subsequent timepoint within the treatment cycle in I-QoL total and domain summary scores.
Treatment response according to EQ-5D-5L	Study Baseline (Treatment Visit) or baseline Week 6 Week 12 EOS Visit.	EQ-5D-5L score	Mean change from study baseline to each subsequent timepoint within the treatment cycle in EQ-5D-5L score
Treatment response according to mPGI-I score	Week 2 Week 6 Week 12 Every 12 weeks thereafter until retreatment EOS Visit.	mPGI-I score	Mean mPGI-I score at each timepoint following each IMP administration
Duration of effect measured by time from previous treatment until next treatment requested (if subsequently found to be eligible for retreatment)	
 • Treatment Visit (Day 1) until date of request of first retreatment (for first treatment cycle) • Retreatment Visit until date of request of next retreatment (for second and subsequent treatment cycles) 	Time to request retreatment	
 • Mean number of days before retreatment is requested • Median number of days before retreatment is requested

Measure	Planned timepoints (dependent on timing of retreatments)	Variable	Endpoint
Duration of effect measured by time from previous treatment until subject is confirmed eligible for next treatment	
 • Treatment Visit (Day 1) until date subject is confirmed as eligible for retreatment (for first treatment cycle) • Retreatment Visit until date subject is confirmed as eligible for next retreatment (for second and subsequent treatment cycles) 	Time to eligibility for retreatment	
 • Mean number of days before eligible for retreatment • Median number of days before eligible for retreatment
Duration of effect measured by time between two treatment administrations	
 • Treatment Visit (Day 1) until first Retreatment Visit (for first treatment cycle) • Retreatment Visit until next retreatment visit (for second and above treatment cycles) 	Time between treatments	
 • Mean number of days between two treatment administrations • Median number of days between two treatment administrations

CIC=clean intermittent catheterisation; DC=detrusor compliance; EFP=end fill pressure; EOS=end of study; EQ-5D-5L=EuroQoL 5-dimension 5-level; IDC=involuntary detrusor contraction; IMP=investigational medicinal product; I-QoL=incontinence quality of life; MCC=maximum cystometric capacity; MDP=maximum detrusor pressure; mPGI-I=modified patient global impression – improvement; PdetMax@1stIDC=maximum detrusor pressure at first involuntary detrusor contraction; Vol@1stIDC=volume at first involuntary detrusor contraction.

7.3 Methods and Timing of Assessing, Recording, and Analysing Efficacy Data

Methods for assessing efficacy data are described below. Timing of efficacy assessments are discussed in [Section 0](#). Procedures for recording efficacy data are discussed in [Section 13.1](#), and methods of analysis are discussed in [Section 9.4.5](#).

7.3.1 Bladder Diary

A 7-day bladder diary will be completed by subjects (with the caregiver's assistance if necessary) at Screening and regularly throughout the study to record the following parameters:

- Weekly number of UI episodes
- Daily urinary frequency (total, spontaneous void only, CIC only)
- 24-hour voided volume (total, spontaneous void only, CIC only)
- Volume per void (total, spontaneous void only, CIC only).

Refer to [Appendix 1](#) for full details regarding bladder diary usage.

7.3.2 Urodynamic Examination

All subjects will have a standardised urodynamic (filling cystometry) assessment at Screening and again at Week 6 following the first IMP administration.

Urodynamics will be conducted according to International Continence Society recommendations [20]. Full details of the urodynamic procedures including standardisation, training, equipment setup, subject preparation, trace annotations, calculations and central review process are contained in a separate Study Specific Urodynamic Manual.

All urodynamic procedures will be covered with a minimum of 2 days of appropriate prophylactic antibiotics. See Section 6.4.1.2 for further details on antibiotic prophylaxis in the study.

All urodynamic data will be reviewed by independent central reviewers to determine the final values for the urodynamic parameters. The central reader's determination will be used for analysis purposes.

During Screening the site will determine if the subject has NDO via the presence of IDCs (inclusion criterion #15); without confirmation from the central reader.

The following urodynamic parameters will be obtained (Table 20):

Table 20 Urodynamic Parameters

Parameter	Unit	Calculation
MCC	mL	Total instilled volume or instilled volume just prior to the terminal IDC minus incontinent volume
MDP	cm H ₂ O	Peak detrusor pressure during storage (filling) phase minus trace baseline pressure
Presence of IDC(s)	N/A	N/A
Vol@1 st IDC	mL	Instilled volume when first IDC commences
PdetMax@1 st IDC	cm H ₂ O	Peak detrusor pressure during first IDC minus trace baseline pressure
EFP	cm H ₂ O	Detrusor pressure at end of filling or just prior to the terminal IDC minus trace baseline pressure
DC	mL/cm H ₂ O	Change in bladder volume divided by change in detrusor pressure (usually measured as MCC divided by EFP)

DC=detrusor compliance; EFP=end fill pressure; IDC=involuntary detrusor contraction; MCC=maximum cystometric capacity; MDP=maximum detrusor pressure; PdetMax@1stIDC=maximum detrusor pressure at first involuntary detrusor contraction; Vol@1stIDC=volume at first involuntary detrusor contraction.

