3.2.2 Secondary Efficacy Endpoints and Evaluations

3.2.2.1 Overview of Secondary Measures

Mean change from study Baseline (assessed at Screening) or from treatment cycle baseline (assessed at Retreatment Assessment Visit) to post-treatment timepoints (timepoints listed in [Table 4](#) and [Table 5](#)):

- Bladder diary measures:
 - weekly number of UI episodes
 - daily urinary frequency (total, spontaneous void only, CIC only)
 - 24-hour voided volume (total, spontaneous void only, CIC only)
 - volume per void (total, spontaneous void only, CIC only).
- Urodynamic filling cystometry measures:
 - maximum cystometric capacity (MCC)
 - maximum detrusor pressure (MDP) during storage
 - volume at first involuntary detrusor contraction (Vol@1stIDC) (subjects without a post-treatment IDC will have their Vol@1stIDC imputed from their MCC)
 - maximum detrusor pressure at first involuntary detrusor contraction (PdetMax@1stIDC)
 - end fill pressure (EFP)
 - detrusor compliance (DC).
- Patient-reported outcome questionnaires:
 - incontinence quality of life (I-QoL) total summary score
 - EuroQol 5-dimension 5-level (EQ-5D-5L)
 - modified patient global impression - improvement (mPGI-I) score (to be assessed at each timepoint without comparison to baseline).

Proportion of subjects at post-treatment timepoints following the first and subsequent treatments with:

- no episodes of UI (i.e. continence is achieved)
- UI response at several levels (i.e. $\geq 30\%$ improvement, $\geq 50\%$ improvement, $\geq 75\%$ improvement etc.)
- no IDCs on urodynamic assessment (i.e. urodynamic cure is achieved).

Duration of effect following the first and subsequent treatments measured by:

- time to request retreatment

- time to eligibility for retreatment
- time between treatments.

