3 EFFICACY AND SAFETY VARIABLES

For the purpose of all analysis, the study baseline is defined as the last value available during screening or day of treatment visit prior to the first study IMP treatment administration (Treatment 1) i.e. prior to the DBPC Cycle. This study baseline will be used in analysis of the efficacy endpoints and the safety endpoints for all treatment cycles.

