6.2 Handling of Dropouts or Missing Data

6.2.1 Analysis Endpoints

6.2.1.1 Efficacy Endpoints

Refer to Section 3.1 and 3.2 for the list of primary and secondary efficacy endpoints and Section 3.2.1 for the list of secondary endpoints used in the hierarchical analysis.

Bladder diary: For data collected from the 7-day bladder diary, if there is 1 or 2 days with no data, the arithmetic means recorded (on the 5 or 6 days that do have events recorded) from the bladder diary parameters will be used for the days with no recorded bladder diary data. If there are more than 2 days of missing data, then the 7-day bladder diary data will be considered invalid.

Statistical Analysis Plan

Version: Final v2.0

September-2018

Ipsen Protocol No. D-FR-52120-222

000000146259

Date of Issue: 21-

Covance Study ID:

Primary efficacy endpoint: No imputation is planned for the primary analysis of the primary endpoint. A sensitivity analysis of the primary efficacy endpoint will be performed using multiple imputations (MI) for missing or invalid data (see Section 7.6.4.3).

Urodynamic secondary efficacy endpoints: All urodynamic data will be reviewed by independent central reviewers to determine the final values for the urodynamic parameters. Only the central reader urodynamic values will be used for analysis purposes. For the secondary efficacy endpoint of Vol@1stIDC, subjects who do not exhibit a post-treatment IDC at Week 6 after the first IMP administration will have Vol@1stIDC imputed using the recorded corrected MCC volume at Week 6.

Quality of life secondary endpoints: For I-QoL total summary score, in accordance with the I-QoL User's Manual (US English version, March 2013), if no more than three items are omitted, a normal arithmetic mean substitution will be computed for these omitted items and imputed to calculate the total summary score. If more than three items are omitted, then there will be no more imputation for those omitted items, and the total summary score will be missing. Similarly, this rule will be applied for each of the domain scores (avoiding and limiting behavior, psychosocial impact, and social embarrassment). These derived scores will be used for analysis, and the investigator recorded eCRF I-QoL total summary score, and each recorded domain score will only be listed.

The formula for the derived scale scores is as follows:

Scale Score = $\{(\text{the sum of the items} - \text{lowest possible score}) / \text{possible raw score range}\} * 100$

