7.6.5 Hierarchical Analysis of Secondary Efficacy Endpoints

As specified in Section 7.6.12, a hierarchical analysis will be performed in the order listed for the following six secondary efficacy endpoints at Week 6 after the first IMP administration:

- 1) Mean change from study Baseline in the MCC
- 2) Mean change from study Baseline in the MDP during storage
- 3) Mean change from study Baseline in the Vol@1stIDC
- 4) Proportion of subjects with no episodes of UI (i.e. continence is achieved)
- 5) Proportion of subjects with no IDCs during storage
- 6) Mean change from study Baseline in the I-QoL total summary score

The Derivation rules are specified in Section 3.2 and Appendix II.

For 1), 2) and 3), an ANCOVA model will be fitted using the “mean change” endpoint, as the response variable to obtain the p-value of treatment groups. The model will be the same as the sensitivity analyses for the primary efficacy endpoint in 7.6.4.2. The LSMEANS of the mean change from study baseline at Week 6 in each group with standard error, the difference of mean between the two treatment groups, the 95% CI of the difference and the p-value for treatment group will be presented.

For 4), a logistic generalised linear mixed model (GLMM) for repeated measures will be fitted for UI responses using repeated measurements at Week 2, Week 6, and Week 12. The “proportion of subjects with no episodes of UI” will be analysed as a response variable, the model will include treatment group, stratification variables, study baseline value, visit (week 2, week 6 and week 12), study baseline*visit and treatment*visit interactions as fixed effect. The study baseline value will be weekly number of UI episodes. The logistic GLMM is fitted using the logit link and the binomial distribution. Odds ratios, 95% CIs of odds ratio, and p-values for treatment group comparisons at each visit (week 2, week 6 and week 12) will be presented.

The SAS codes of GLMM for reference are below.

```
CCI
[Redacted SAS code]
```

CCI
[Redacted]
[Redacted]
[Redacted]

For 5), a logistic regression model will be performed with “proportion of subjects” as the response variable. The model will include treatment group, and stratification variables.

Odds ratio, 95% CI of odds ratio, and p-value will be presented.

The SAS codes of logistic regression for reference are below.

CCI
[Redacted]
[Redacted]
[Redacted]
[Redacted]
[Redacted]
[Redacted]
[Redacted]
[Redacted]

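### Does a subject whose central baseline read shows no involuntary detrusor contraction fall out of the Vol@1stIDC test, and does the plan need changing for it?

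*Protocol*

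**What the plan says.** Protocol 7.3.2 separates two uses of the screening cystometry. The site judges IDCs for eligibility, "without confirmation from the central reader". Independent central readers determine the values for analysis, and SAP 6.2.1.1 repeats this without any fallback to the site value: "Only the central reader urodynamic values will be used for analysis purposes".

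Table 20 of the Protocol defines Vol@1stIDC as the volume instilled at the start of the first IDC, so it has no value when no IDC is read. Both documents foresee this after treatment. Protocol 3.2.2.1 says "subjects without a post-treatment IDC will have their Vol@1stIDC imputed from their MCC", and SAP 3.2 has the same rule. SAP 6.2.1.1 ties it to one visit: "subjects who do not exhibit a post-treatment IDC at Week 6 after the first IMP administration will have Vol@1stIDC imputed", using the Week 6 MCC.

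Change from baseline in Vol@1stIDC is third of the six ordered secondary endpoints. SAP 7.6.5 analyses it by ANCOVA: "The model will be the same as the sensitivity analyses for the primary efficacy endpoint in 7.6.4.2". On where the definitions sit, the same section says: "The Derivation rules are specified in Section 3.2 and Appendix II".

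Endpoint 5, the proportion with no IDCs at Week 6, uses logistic regression: "The model will include treatment group, and stratification variables".

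**The concern.** Eligibility rests on one reading and analysis on another, so some randomised subjects may have a screening trace that the central reader calls free of IDCs. Such a subject has no baseline Vol@1stIDC under the visible rules, hence no change score, and leaves the endpoint 3 model even with complete Week 6 data. Endpoint 3 is a gate: if it fails, endpoints 4 to 6 become descriptive. A confirmatory analysis set would then depend on a convention that the visible text does not state.

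On endpoint 5, a subject with no centrally read IDC at either visit counts as a urodynamic cure although the central reader never saw the abnormality. If such subjects respond alike in every arm, the cure rate rises throughout where their IDC-free rate exceeds the true rate, and the contrast shrinks.

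**Working it through.** **Does any visible rule rescue the subject?** No.
- SAP Section 3 says "the study baseline is defined as the last value available during screening" or on the treatment day before dosing. Protocol Table 4 schedules one pre-treatment urodynamic assessment, so there is normally no other value to take.
- Multiple imputation is described for the primary endpoint only (SAP 6.2.1.1 and 7.6.4.3).
- The missing-at-random statement in SAP 6.2.1.1 concerns missing outcomes under a repeated-measures model. It does not supply a missing baseline.
- The ANCOVA in SAP 7.6.4.2 is written with baseline incontinence episodes as covariate. Whichever baseline is used as covariate, the response is a change and needs a baseline Vol@1stIDC.

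**The plan's own figure, for context.** The only sample size stated is for the primary endpoint: difference 9, SD 20, alpha 0.025 two-sided, power 80%. The normal formula gives n = 2 × (20/9)² × (2.241 + 0.842)² = 94 per group. The noncentral t gives 96 with power 80.4%, which matches the stated 96. No effect size, SD or power is given for Vol@1stIDC.

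**Size of the loss on endpoint 3.** Inputs from the documents are 110 per arm and 10% dropout to Week 6, giving 110 × 0.90 = 99 evaluable per arm. Assumed: the share *d* with no centrally read baseline IDC, and starting powers of 80% or 90% at alpha 0.05.
- Standard error factor: 1/√(1 − d).
- Power after loss: Φ[(z_α + z_β)√(1 − d) − z_α], with z_α = 1.960 and z_β = 0.842 (80%) or 1.282 (90%).

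| d | remaining per arm | SE rise | from 80% | from 90% |
|---|---|---|---|---|
| 1% | 98 | 0.5% | 79.6% | 89.7% |
| 2% | 97 | 1.0% | 79.2% | 89.4% |
| 5% | 94 | 2.6% | 78.0% | 88.5% |
| 10% | 89 | 5.4% | 75.7% | 86.8% |

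If only one dose passes the primary test, the hierarchy runs at 0.025. At an assumed standardised difference of 0.45, power there is 82.2% with no loss, 80.1% at d = 5% and 77.7% at d = 10%.

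**Would substituting baseline MCC do better?** Let *r* be the treatment effect in the affected subjects relative to the rest, with equal residual variance. Keeping them multiplies the average effect by 1 − d(1 − r) and leaves the standard error alone. Dropping them keeps the full effect but multiplies the signal-to-noise ratio by √(1 − d). Substitution wins only if 1 − d(1 − r) > √(1 − d), that is, r > 1 − [1 − √(1 − d)]/d.
- d = 5%: r > 1 − 0.0253/0.05 = 0.49.
- d = 10%: r > 1 − 0.0513/0.10 = 0.49.

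Starting from 80% power:

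| | d = 5% | d = 10% |
|---|---|---|
| dropped | 78.0% | 75.7% |
| kept, r = 1 | 80.0% | 80.0% |
| kept, r = 0.5 | 78.0% | 75.9% |
| kept, r = 0 | 75.9% | 71.3% |

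The documents do not give r. The substituted baseline is a censored value, and a subject without an IDC at either visit would contribute the change in MCC, which is endpoint 1.

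**Endpoint 5.** With true rates p₁ and p₀ and a common IDC-free rate q in the affected subjects, the observed rate in each arm is (1 − d)p + dq. The contrast is (1 − d)(p₁ − p₀): an assumed 40% versus 20% becomes 19 points at d = 5% and 18 points at d = 10%. A supplementary analysis in subjects with a centrally read baseline IDC, or a table of disagreements, leaves the hierarchical test as it is and recovers none of this.

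**Error rate.** The central baseline status describes a trace recorded before randomisation. Leaving out subjects on that basis compares randomised groups within a subset fixed in advance, provided the baseline reading is blind to allocation.

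**The case for a change.** The best case for acting is that the sponsor saw that Vol@1stIDC is undefined without an IDC, wrote a rule for Week 6, and then let the site-central split create the same possibility at baseline, where no rule is visible. A gated endpoint should not rest on a choice made once the data are known, and stating the rule costs a sentence.

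The textual part stands: the substitution is limited to post-treatment in all three places where it appears. The rest is weaker. The SAP sends detailed endpoint definitions to Appendix II, and Protocol 7.3.2 sends calculations and central review to a separate urodynamic manual. A baseline convention belongs in those two places, and neither is public, so its absence here is not evidence that the plan lacks one. If it is absent, SAP Section 1 has the SAP and any amendment final before database lock, so a convention can still be fixed before unblinding. The two obvious choices, dropping the subject or using baseline MCC, are both defensible and differ little at low disagreement rates.

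Reading locally for eligibility and centrally for analysis is a normal trade-off, since waiting for a central read would lengthen screening. Endpoint 5 is defined by Week 6 status and needs no baseline IDC; cure is a label there.

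**Conclusion.** The visible text leaves a derivation detail open, and no change to the plan follows. Under that text, a subject with no centrally read baseline IDC has no endpoint 3 change score. How many there would be is unknown. Across assumed disagreement of 1% to 10%, 80% power falls to between 79.6% and 75.7%, with no type I inflation as long as baseline reads are blind to allocation. The natural remedy is not shown to help: it beats dropping the subjects only when their relative treatment effect exceeds about 0.49. The endpoint 5 additions would be optional reporting and would not alter the test. All of this rests on assumed disagreement rates, assumed starting power and equal residual variance. It also allows that Appendix II or the urodynamic manual may already hold the baseline rule. An analyst who finds none there can settle the convention before unblinding.
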